Secondary Objectives	1. Rate of brain metastases following TTField therapy at 12 months. 2. Overall survival of participants with SCLC after using TTField therapy. 3. TTField therapy related side-effects. 4. Quality of life among participants using TTField therapy. 5. Observed rate of brain metastases 6-month from the beginning of the 4 th cycle of chemotherapy to development of brain metastases
Primary Endpoints	Incidence of SCLC brain metastases at 6 months from the start of TTField therapy
Secondary Endpoints	1. Incidence of SCLC brain metastases at 12 months 2. Overall survival 3. Incidence of TTfield related adverse events 4. Quality of life 5. Incidence of SCLC brain metastases at 6 month from the beginning of the 4 th cycle of chemotherapy to development of brain metastases

	metastases
Number of Participants	A total of 106 participants will be enrolled in this study. Among these, target enrollment will include 45 participants with extensive stage disease, and 61 participants will have limited stage disease.
Duration of Therapy	Participants will receive TTField therapy for 12 months, or until development of brain metastases, whichever comes first.
Duration of Follow Up	Participant followed up will continue until death.
Inclusion Criteria	
 • ≥ 22 years of age • Biopsy-proven SCLC • Clinical Response to standard of care chemo- and/or radiotherapy, as defined by no thoracoabdominal tumor progression on CT imaging within 12 weeks prior to enrollment. • No contraindications to treatment with Optune®. • No other active malignancies, with exception of non-metastatic prostate cancer, treated Stage I breast cancer, skin malignancies • No brain metastases [gadolinium MRI < 12 weeks before enrollment]. • No mental conditions that would prevent compliance. • Life expectancy of at least 3 months. • ECOG ≤ 2.
Exclusion Criteria	
 • Progressive disease. • Pregnant • Implanted pacemaker, programmable shunts, defibrillator, deep brain stimulator, other implanted electronic devices in the brain, or documented clinically significant arrhythmias. • Evidence of increased intracranial pressure (midline shift > 5mm, clinically significant papilledema, vomiting and nausea or reduced level of consciousness)

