3.2 STUDY ENDPOINTS

PRIMARY ENDPOINT

Objective	Endpoint	Start	End
Observed rate of brain metastases following TTFields therapy at 6 months	Incidence of SCLC brain metastases at 6 mo	Start of TTFields [baseline]	6 mo

SECONDARY ENDPOINTS

Objective	Endpoint	Start	End

Observed rate of brain metastases following TTFields therapy at 12 months	Incidence of any SCLC brain metastases at 12 mo	Start of TTFields [baseline]	12 mo
Overall survival of participants with SCLC after using TTFields therapy.	Overall survival	Start of TTFields [baseline]	Death or last follow-up at 60 months.
TTFields therapy related side effects.	1. Incidence of TTFields related AEs 2. Incidence of cognitive AEs using Mini Mental State Exam (MMSE)	Start of TTFields [baseline]	12 mo 6, 12 mo 12 mo
Quality of life among participants using TTFields therapy.	EORTC QLQ-C30 questionnaire at 6 and 12 mo	Start of TTFields [baseline]	6, 12 mo
Observed rate of SCLC brain metastases at 6 month from the beginning of the 4 th cycle of chemotherapy to development of brain metastases	Incidence of SCLC brain metastases at 6 month from the beginning of the 4 th cycle of chemotherapy to development of brain metastases	Start of the 4 th cycle of chemotherapy [baseline]	6 mo

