7.6 FOLLOW-UP

Aside from clinical follow-up at 1 and 3 months after completion of TTField therapy, all subsequent follow-up, including imaging studies, clinical evaluations, and any laboratory procedures will be consistent with institutional standard of care oncology follow-up visit. Starting from the last chemo-radiotherapy treatment for the primary tumor, these standard of care oncology follow-up visits should occur every 3 to 4 months during years 1 and 2, and then every 6 months thereafter. All participants will be followed (via medical record, or by other means such as a phone call) for survival status following TTField therapy discontinuation at 6, 12, 24, 36, and 60 months.

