^DInitial imaging at screening must be within 12weeks prior to the first dose of TTField therapy. Scans performed as part of routine clinical management are acceptable for use as the screening scan if they are of diagnostic quality and performed within 12 weeks prior to the first dose of trial treatment. Measurable disease based on RECIST 1.1 must be confirmed by investigator and/or radiologist before enrollment.

^EThe investigator, or other qualified designee, will provide participants, as well caregiver or family member (if needed), with training and instruction on how to operate the Optune® device for continuous at-home treatment.

^FAny additional on-study hematological and biochemical assessments will only be performed per physician's discretion, if clinically indicated.

^G For persons of reproductive potential, a urine pregnancy test should be performed within 72 hours prior start of trial treatment. Persons will be asked pregnancy status thereafter at the beginning of every treatment cycle. If persons are unsure, then a urine pregnancy test will be performed within 72 hours prior to the next trial cycle. If urine pregnancy results cannot be confirmed as negative, a serum pregnancy test performed by the local study site laboratory will be required. Pregnancy tests (serum and/or urine tests) should be repeated, if required, per institutional guidelines.

^H AEs and laboratory safety measurements will be graded per NCI CTCAE version 4.03. All AEs, whether gradable by CTCAE or not, will also be evaluated for seriousness. Record all AEs occurring within 30 days after the last trial treatment. Report all SAEs (related and unrelated to trial treatment) occurring up until 90 days after the last dose of trial treatment, or the start of new anti-cancer treatment, whichever comes first.

Afterwards, report only SAEs that are related to trial treatment.

^I QoL assessments will be administered before start of treatment (baseline), at 28 weeks, and again at end of treatment (12 months).

^J All participants will be followed for survival status following TTField therapy discontinuation at 6, 12, 24, 36, and 60 months.

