8.4 EVALUATION OF SURVIVAL

Overall Survival: Overall Survival (OS) is defined as the time from start of TTFields therapy (Day 1) to death due to any cause, or last follow-up at 60 months.

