The distribution of overall survival will be graphically described using Kaplan-Meier plot, for all subjects together, and for each disease group (extensive stage and limited stage). If estimable, the median survival time will be reported with 95% confidence interval. The analysis is just for description. No hypothesis testing is planned for this endpoint. However, we will fit two cox

proportional hazard regression model to identify risk factors that may impact the OS. Covariates evaluated in the univariable analysis in Section 10.2.1 will also be evaluated in the cox proportional hazard regression model. OS at 6, 12, 24, 36 and 60 months after completion of TTField therapy will be reported.

We will estimate TTField therapy-related toxicity and along with an exact confidence interval using the safety set. A summary table of observed AEs will also be reported by disease group (extensive stage and limited stage).

The Quality of life scores will be recorded over time (See Section 7.8 for details) using the EORTC QLQ-C30 questionnaire. Summary of QoLs and its change over time will be presented graphically using box plot and spaghetti plot, in addition to a summary table of QoL over time. No hypothesis testing is planned for QoL.

Incidence of cognitive AEs will be assessed by measuring changes in MMSE scores over time. Descriptive statistical analysis will be conducted on the endpoint. (See Section 7.8 for details on time points for measurement)

To evaluate how the time of last cycle of chemotherapy or chemoradiation therapy impact our observed incidence of SCLC brain metastases, we will also conduct a parallel analysis using SCLC brain metastases rate at 6-month from the beginning of the 4th cycle of chemotherapy to development of brain metastases as a secondary endpoint. We will use exactly the same approach as described in Section 10.2.1.

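### The five OS landmark rates in Section 10.2.2 are timed from completion of device therapy, whereas OS is defined from Day 1, so as written they are not OS as defined

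*Combined protocol and SAP*

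**What the plan says.** - **Definition.** Section 8.4 has OS "defined as the time from start of TTFields therapy (Day 1) to death due to any cause, or last follow-up at 60 months". The endpoint table in Section 3.2 also starts OS at the start of TTFields and gives its end as "Death or last follow-up at 60 months".
- **Analysis.** Section 10.2.2 plans a Kaplan-Meier plot overall and by stage, the median with a 95% confidence interval, and Cox models. It calls the analysis descriptive, with no hypothesis test, and then adds: "OS at 6, 12, 24, 36 and 60 months after completion of TTField therapy will be reported".
- **Follow-up.** Section 7.6 collects "survival status following TTField therapy discontinuation at 6, 12, 24, 36, and 60 months", and the footnote on survival status in Section 7.8 repeats this schedule. Section 7.8 also records survival status during the treatment period.
- **Length of therapy.** The Synopsis says "Participants will receive TTField therapy for 12 months, or until development of brain metastases, whichever comes first". Sections 4.6, 6.1, 6.2 and 6.3 describe further or different circumstances in which therapy ends early.
- **Population and missing data.** Section 10.1 makes all who initiated therapy evaluable for efficacy. Section 10.4 rules out imputation and allows a participant's data to be left out wholly or in part where they do not suffice for an endpoint.

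**The concern.** One endpoint has two time origins, and nothing in the document reconciles them or labels the second as a separate post-therapy analysis.

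End of therapy is a poor origin for an OS rate. It happens after baseline and depends on how the participant fares. It comes at 12 months for some and earlier for others, and a participant who dies on the device never completes. The plan does not say how on-therapy deaths or early stoppers enter the five rates. An analyst could leave them out for want of a completion date, count them as dead at time zero, or ignore the phrase and use Day 1. These choices give different numbers from the same data.

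At stake is the meaning of the survival percentages that the report will carry. In a single-arm study such rates tend to be set beside outside series, and that needs a common origin and a denominator of everyone treated.

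**Working it through.** The plan states no OS rate, event count or OS power, so there is no figure to reproduce. The check is a comparison of definitions, followed by an illustration of size.

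**1. Origins side by side**

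| Place | Clock starts | Times |
|---|---|---|
| 3.2, 8.4 (definition) | Day 1 | to death or last follow-up at 60 months |
| 10.2.2 (landmark rates) | completion of therapy | 6, 12, 24, 36, 60 months |
| 7.6, 7.8 footnote (contacts) | discontinuation of therapy | 6, 12, 24, 36, 60 months |

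The landmarks and the contacts share the same five times, so the contact schedule was probably carried into the analysis text. Completion and discontinuation are not the same event. After a full 12-month course, the last landmark falls at 12 + 60 = 72 months from Day 1, past a 60-month end counted from Day 1.

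**2. Inputs for the illustration**

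- Extensive stage: Section 1.1 gives a median of 9 to 10 months from diagnosis; 9.5 is used.
- Limited stage: Section 1.1 gives a survival time of about 18 months, without calling it a median or naming its origin; it is taken as a median.
- Group sizes: 45 and 61 (Section 10.1).
- Assumptions: these figures apply from Day 1, survival is exponential, and therapy lasts 12 months unless death comes first.

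**3. Formulas**

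- OS from Day 1: S(t) = 0.5^(t/median).
- Completers-only rate t months after a 12-month course: S(12 + t)/S(12).

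**4. Results**

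| | Extensive, 9.5 months | Limited, 18 months |
|---|---|---|
| S(12) | 0.417 | 0.630 |
| Dead before month 12 | 58% (about 26 of 45) | 37% (about 23 of 61) |
| OS from Day 1 at month 18, S(18) | 26.9% | 50.0% |
| Completers only, 6 months after completion, S(18)/S(12) | 64.5% | 79.4% |
| OS from Day 1 at month 6, S(6) | 64.5% | 79.4% |

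At the same elapsed time, the completers-only rate can never be below OS from Day 1, because S(12) is at most 1. Against the same-numbered Day 1 landmark (last row), the exponential difference is exactly zero.

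**5. Sensitivity to hazard shape**

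Use Weibull survival, S(t) = 0.5^((t/median)^k). The 12-month rate from Day 1 and the rate 12 months after completion are:

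| k | Extensive: Day 1 / post-completion | Limited: Day 1 / post-completion |
|---|---|---|
| 0.8 | 43.4% / 53.8% | 60.6% / 69.0% |
| 1.0 | 41.7% / 41.7% | 63.0% / 63.0% |
| 1.2 | 40.0% / 30.4% | 65.3% / 57.5% |

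The direction is therefore not fixed.

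Over k = 0.8 to 1.2, the share dead before month 12 is 55% to 62% (25 to 28 of 45) for extensive-stage medians of 9 to 10 months, and 35% to 39% (21 to 24 of 61) for a limited-stage median of 18. With wider medians it is 50% to 80% (extensive, 6 to 12 months) and 26% to 50% (limited, 12 to 24 months).

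**The case against.** The strongest reply is that this is loose wording in one descriptive sentence. The Kaplan-Meier plot, median and Cox models name no other origin and so follow Section 8.4; survival from Day 1 at any month can be read off that curve. No test, significance level or sample size depends on OS. The sentence also states its own anchor, so a careful reader would not mistake it. And Sections 3.2 and 8.4 could mean, by last follow-up at 60 months, the final contact in Section 7.6, which would remove the month-72 conflict. All of this limits the harm. It does not give the five rates the defined origin.

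Three stronger readings are tempting, and the documents do not support them.

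- **That on-therapy deaths are excluded.** No section says so. Section 10.1 counts all initiators, Section 7.6 follows all participants from discontinuation, and a death on therapy could be counted as zero post-therapy survival. Exclusion is what a literal reading of completion leads to, and Section 10.4 leaves room for it, but it is one reading.
- **That the wording turns a 6-month rate of about 65% into 27%, or 79% into 50%.** Setting S(6) beside S(18) only compares two points on one Day 1 curve. Conditioning on completion gives 64.5% and 79.4%, the same as S(6) under exponential survival.
- **That this is immortal-time bias.** That bias arises when guaranteed survival time is counted as follow-up. A clock that starts at completion counts none. The problem is a conditional quantity with staggered origins.

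Nor can one say that survival from Day 1 must be shorter than the background figures. Day 1 comes after diagnosis, but Section 4.1 selects responders without brain metastases, which pulls the other way.

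**Conclusion.** The point holds and should be corrected. Sections 3.2 and 8.4 conflict with Section 10.2.2 on the time origin of OS, and the five landmark rates as written are not OS as defined. Taken literally they describe survival after therapy among those who reach its end, with a time zero that differs between participants.

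Under the stated assumptions, the group that never reaches a 12-month completion is large: more than half of extensive-stage and more than a third of limited-stage participants. At month 18 the choice between completers only and all initiators is worth 64.5 − 26.9 = 37.6 percentage points in extensive stage and 79.4 − 50.0 = 29.4 in limited stage. These sizes rest on background medians that the protocol does not state from Day 1, so they are illustrative; the conflict itself rests on no assumption. No general statement about over- or understatement against the same-numbered Day 1 landmark is warranted. The consequence is confined to five descriptive rates for a secondary endpoint.

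**What to change.** - **Section 10.2.2:** report Kaplan-Meier estimates of OS at 6, 12, 24, 36 and 60 months from the start of TTField therapy (Day 1), among all who initiated therapy, overall and by stage.
- **If survival after therapy is also wanted:** name it a separate conditional analysis, define its origin (completion or discontinuation) and its denominator, and say how on-therapy deaths and early stoppers enter.
- **Section 7.6 and the survival-status footnote in Section 7.8:** state that contacts timed from discontinuation only update vital status and date of death, and say how they fit with the 60-month end of OS in Sections 3.2 and 8.4.

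The cost is one sentence in the analysis section and a clarification in two places. No new data are needed. Survival status is already recorded during treatment and afterwards, and a contact 60 months after discontinuation can never fall before month 60 from Day 1.

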Investigational Product(s)	Optune® is a portable battery powered device that produces alternating electrical fields, termed tumor treatment fields (“TTFields”) within the human body. These TTFields are applied to the patient by electrically insulated surface transducer arrays, which function to disrupt the rapid cell division of cancer cells.
Statistical Considerations	
Primary Evaluations: Incidence of brain metastases 6 months after start of Optune®
 
Sample Size (statistical assumptions) For extensive stage, we need 45 subjects for 80% power to detect a 50% reduction at a 5% significance level using a test for one proportion, assuming the incidence rate is 40% for subjects not receiving Optune®.
 
For limited stage, we need 61 subjects for 80% power to detect a 50% reduction at a 5% significance level, using a test for one proportion, assuming the incidence rate is 30% for subjects not receiving Optune®.

Efficacy Endpoints

- Presence of brain metastasis at 6 and 12 months
- Overall Survival
- Incidence of SCLC brain metastases at 6 month from the beginning of the **4th cycle of chemotherapy to development of brain metastases**

Safety Endpoints:

- Quality of life questionnaire
- Side effects, particularly cognitive side effects (mental status exam and questionnaire)

SCHEMATIC OF STUDY DESIGN

[figure not shown]

Figure 1. Study Overview.

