1.3 RATIONALE

SCLC is a common disease, with a high propensity for brain metastases. Although the use of PCI has for a long time been considered a standard therapy for patients with both LS-SCLC and ES-SCLC, recent results from a randomized trial examining PCI vs observation with frequent use of brain MRI imaging, revealed no difference in outcomes.¹⁸ The findings of this study have changed the practice in large academic institutions overnight (*personal communication*), and patients with ES-SCLC are no longer offered PCI as a standard of care in many academic centers in the United States. Large cooperative groups are planning to start a similar randomized trial for patients with LS-SCLC. Overall, this leaves patients with very limited treatment options, and given the high risk of brain metastases, the need for novel therapies is greatly needed.

TTFields therapy has entered the oncology treatment landscape as an FDA-approved cancer treatment for recurrent GBM and is part of the National Comprehensive Cancer Network (NCCN) Treatment Guidelines for this disease. The success of this approach in reducing the risk of recurrent GBM has been adopted in the randomized phase 3 METIS trial for patients with known brain metastases from NSCLC, which is currently on-going at many US centers. We hypothesize that TTFields can be similarly adapted to prevent the formation of SCLC metastatic brain lesions. TTFields therapy is shown to be safe and lacks the conventional cytotoxic systemic side effects. Thus this alternative interventional could significantly decrease the brain metastatic rate as well as lower the need for toxic whole brain irradiation

This study will evaluate the potential for TTFields therapy as a novel approach to reducing the rate of in-brain failures in patients with SCLC that have completed standard-of-care chemo-radiotherapy. It is hypothesized that TTFields therapy can be used prophylactically to reduce the incidence of brain metastases as compared to historical observational reports, and have no effect on the cognitive function of those receiving this treatment modality.

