Participants with either LS-SCLC or ES-SCLC must be no more than 6 weeks from having received last dose of chemotherapy for primary tumor (per institutional guidelines), and must have at least demonstrated a partial response to treatment, to be considered eligible for TTField therapy with the Optune® device. Participants are encouraged to undergo TTField therapy (200 kHz) for a minimum of 18 hours per day for a period of 12 months, or until the confirmed appearance of metastatic brain lesions, whichever comes first. Participants that develop numerous (>10) supratentorial metastatic lesions before 12 months will discontinue further use of TTFields and will receive palliative/supportive care per institutional guidelines (e.g., whole brain radiotherapy). Participants that develop either limited (≤ 10) supratentorial or any number of infratentorial metastases will remain eligible to continue with TTFields therapy for the duration of the 12 months after the brain metastatic lesions are addressed according to institutional guidelines (e.g. partial brain irradiation stereotactic radiosurgery, stereotactic body radiation therapy). Systemic progression will be managed per institutional guidelines (e.g. systemic chemotherapy, immunotherapy, radiation therapy, etc.) and patients will remain eligible to continue with TTFields therapy for the duration of the 12 months. While on-study, participants will be clinically evaluated every 2-3 months per NCCN guidelines and will all be monitored remotely by phone calls monthly and will undergo gadolinium (gd)-MRI of the head at 6 months to assess occurrence of disease progression (per RECIST v1.1). Participants will be subject to periodically answering quality of life (QoL) questionnaires (i.e., baseline, 6 and 12 months after initiating treatment). At the end of study, participants will undergo clinical follow-up 1 and 3 months after completion of TTField therapy. Subsequent follow-up until death (up to 5 years) will be in accordance with standard of care (i.e., every 3 months during years 1 and 2 following last chemo-radiotherapy, then every 6 months thereafter).

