6.3 TREATMENT PERIOD AND MAINTENANCE

Participants will receive TTField therapy on continuous basis (i.e., 18-24 hours a day, 7 days a week) for a period of 12 months. Participants that develop supratentorial metastatic lesions (>10) before 12 months will discontinue further use of TTFields and will be provided supportive/palliative treatments and supportive care (e.g., management of radionecrosis) consistent with institutional standard of care (e.g., whole brain radiation therapy). Participants that develop either limited (≤ 10) supratentorial or any number of infratentorial metastases will remain eligible to continue with TTFields therapy for the duration of the 12 months after the brain metastatic lesions are addressed according to the institutional guidelines (e.g. partial brain irradiation, stereotactic radiosurgery, stereotactic body radiation therapy). These participants will be clinically monitored per institutional guidelines. Participants that develop systemic progression, which can be treated per institutional standard of care (e.g. systemic chemotherapy, immunotherapy, radiation therapy, etc.), may remain eligible to continue with TTField therapy for the duration of the 12 months treatment period. Information regarding systemic therapy must be recorded in CRF.

After 12 months study period, participants will not be able to stay on the TTField therapy, and will be clinically monitored per institutional guidelines.

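### MMSE change is reported as device cognitive safety without separating assessments made before and after brain metastasis or cranial radiotherapy

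*Combined protocol and SAP*

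**What the plan says.** **Hypothesis and endpoint.** Section 1.3 hypothesises that the device will "have no effect on the cognitive function of those receiving this treatment modality". Section 3.2 gives the objective as "TTFields therapy related side effects" and lists two endpoints under it: device-related adverse events, and cognitive adverse events measured by MMSE. The synopsis also lists cognitive side effects among the safety endpoints.

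**Analysis.** Section 10.2.2 states "Incidence of cognitive AEs will be assessed by measuring changes in MMSE scores over time" and adds "Descriptive statistical analysis will be conducted on the endpoint". It defines no MMSE drop that counts as a cognitive adverse event. It gives no cut-off or stratification at brain metastasis or radiotherapy.

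**Timing and data.** Table 3 in Section 7.1 schedules MMSE at baseline, 6 months and 12 months, and labels the last of these as end of treatment (EOT). Section 10.1 counts everyone who started TTFields as evaluable for safety. Section 10.4 uses all available data where possible and imputes none.

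**Participants with brain metastases.** Section 3.1 says "Participants that develop either limited (≤ 10) supratentorial or any number of infratentorial metastases will remain eligible to continue with TTFields therapy" once the lesions have been treated, and its examples include partial-brain irradiation and radiosurgery. Section 6.3 agrees. Section 6.6 allows radiation and systemic anti-cancer therapy alongside the device. Participants with more than 10 supratentorial lesions stop the device, and whole-brain radiotherapy is given as an example of their later care. Section 4.6 differs: it removes participants with supratentorial lesions from the study and lets those with infratentorial or systemic metastases continue.

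**The concern.** A brain metastasis, or radiation given for one, may itself lower cognition. Brain metastasis is also the trial's primary event, so it will occur in a foreseeable part of the sample between the baseline and later MMSE assessments. A fall in MMSE after such an event would then sit, under a device side-effect heading, beside a fall in a metastasis-free device wearer.

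There is no control arm to absorb this. If decline is more common after metastasis or brain radiotherapy, the pooled figure also depends on efficacy: with the same true device effect on cognition, a device that failed to prevent metastases would look cognitively worse than one that succeeded. At stake is whether the trial can say anything useful about the cognitive hypothesis in Section 1.3.

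**Working it through.** **1. The plan's own figures.** Section 10.3 gives 45 extensive-stage participants (40% against 20%) and 61 limited-stage participants (30% against 15%), for 80% power with a two-sided exact test at 5%. With at most 2.5% in each tail:
- n = 45: reject at 11 or fewer events; attained alpha 0.034, power 0.826.
- n = 61: reject at 11 or fewer events; attained alpha 0.049, power 0.804.

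These are the smallest sizes that reach 80%, so the plan's numbers reproduce. The documents give no figure for MMSE.

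**2. Participants with brain metastases by 6 months** (number × rate, everyone followed):
- Target rates: 45 × 0.20 + 61 × 0.15 = 9.0 + 9.15 = 18.15, or 17% of 106.
- Null rates: 45 × 0.40 + 61 × 0.30 = 18.0 + 18.3 = 36.3, or 34% of 106.

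About 88 (106 − 18) to 70 (106 − 36) would be metastasis-free at 6 months. Deaths and missed tests reduce all these counts.

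**3. Why no 12-month share is given.** A constant hazard without deaths, 1 − (1 − p)², gives:
- Target: 45 × 0.36 + 61 × 0.2775 = 33.1.
- Null: 45 × 0.64 + 61 × 0.51 = 59.9.

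Section 1.1 puts median survival from diagnosis at 9 to 10 months (extensive) and about 18 months (limited). As a rough check, assume exponential survival with medians of 9.5 and 18 months:
- Extensive: 45 × 0.5^(12/9.5) ≈ 19 alive at 12 months.
- Limited: 61 × 0.5^(12/18) ≈ 38 alive at 12 months.

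The total is about 57, below the upper count of 60. Enrolled responders may live longer, but the counts clearly do not measure MMSE data at 12 months. Device stoppage reduces those data further.

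**4. Possible effect on the 6-month result.** The decline rates here are assumptions, not taken from the documents: q0 = 5% to 10% without metastasis and q1 = 20% to 50% after metastasis or brain radiotherapy. With b the share with metastases, the pooled rate is b·q1 + (1 − b)·q0.

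| | b | lowest (q0 5%, q1 20%) | highest (q0 10%, q1 50%) |
|---|---|---|---|
| Target | 0.171 | 7.6% | 16.8% |
| Null | 0.342 | 10.1% | 23.7% |

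At fixed rates of 5% and 30%, the pooled figure is 9.3% at target and 13.6% at null, although the rate in metastasis-free participants is 5% in both. This assumes that participants with metastases complete the test as often as the others. If the sickest drop out, the effect is smaller.

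**The case against.** Several counter-arguments have force.

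- **The plan does not order pooling.** A reader might infer that every MMSE fall must count equally. The text does not say so: Section 10.2.2 is silent, no cognitive-event threshold is set, and only the objective's label in Section 3.2 carries the claim of relatedness. What stands is that, with Sections 10.1 and 10.4, one summary of all participants is the natural reading.
- **Causality is graded.** Section 9.2 requires a clinician's causality grade for collected adverse events, Section 9.5 records relationship to the study product, and Section 10.2.2 estimates therapy-related toxicity. A pre-event summary is therefore not the only safeguard. The grading is partial, because cognitive events are derived from MMSE change and nothing links that change to it.
- **Whole-brain radiotherapy may contribute little.** A reader might infer that the result will be full of MMSE scores taken after it. Participants who stop the device return for an EOT visit (Section 4.6) at 10 ± 10 days (Section 7.5), and Table 3 ties the last MMSE to EOT. Many may have no MMSE scheduled well after whole-brain treatment. The clearer route is participants who continue the device after focal treatment.
- **The pre-event row is selected.** It conditions on a post-baseline event and favours healthier participants. This stands, and it is why that row should not replace the all-participant summary.
- **The endpoint is descriptive and secondary.** It is not tested, and no stopping rule in Section 9.7 uses it. This limits the weight of the point, but a descriptive table under a side-effect label will still be read as device safety.

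**Conclusion.** The point holds as a modest, cheap improvement. As written, the MMSE analysis can mix effects of brain metastasis and brain radiotherapy into the device's cognitive-safety result. At the design's own rates, about 18 to 36 of 106 participants would have brain metastases by 6 months, before deaths and missed tests. The direction of the distortion assumes that decline is more common after these events. Its size depends on decline rates that the documents do not give and on who completes the test.

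Three stronger readings are not supported. A 12-month share of 31% to 57% (33 to 60 of 106) might be inferred from a constant hazard, but it ignores deaths and device stoppage. The QLQ-C30 display does not need the same split on this ground, because Section 3.2 frames it as quality of life among users rather than attribution to the device. Splitting MMSE would not settle the hypothesis in Section 1.3 either, since prior and concurrent systemic therapy remain in a single-arm comparison with baseline.

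**What to change.** In Section 10.2.2:

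1. Keep the all-participant summary of MMSE change.
2. Beside it, report MMSE change in two rows: assessments before, and assessments after, first brain metastasis or any cranial radiotherapy, whichever comes first. Give the number assessed in each row at 6 and 12 months.
3. Base any statement about a device effect on cognition on the pre-event row read together with the all-participant row.
4. State the limits: fewer observations in the pre-event row; a selected, healthier subset; metastases not yet detected between the 3-monthly MRIs still included; prior or concurrent systemic therapy not removed.

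Confirm that the CRF captures cranial-radiotherapy dates. Section 6.3 requires systemic therapy to be recorded and Section 6.4 covers medications, but no section expressly requires these dates.

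Section 4.6 must be reconciled with Sections 3.1, 6.3 and 6.6 on whether participants with supratentorial lesions stay on study, because this decides who supplies later MMSE values.

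The cost is analysis-plan wording, one table split and possibly one CRF field. No visit or test is added.
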